# JHM IRB - eForm A - Protocol

• Use the section headings to write the JHM IRB eForm A, inserting the appropriate material in each. If a section is not applicable, leave heading in and insert N/A.

• When submitting JHM IRB eForm A (new or revised), enter the date submitted to the field at the top of JHM IRB eForm A.

\*

#### 1. Abstract

a. Provide no more than a one page research abstract briefly stating the problem, the research hypothesis, and the importance of the research.

African Americans (AAs) are disproportionately affected by incident, advanced and progressive chronic kidney disease (CKD); including a 3 to 4-fold greater risk of end-stage renal disease (ESRD) and earlier onset of ESRD when compared to whites. Racial disparities in CKD are most profound among persons of low socioeconomic status (SES), and dietary factors (limited availability of healthy foods and unhealthy dietary patterns) likely underlie much of this disparity. Low SES AAs are more likely to experience food insecurity (the inability to afford nutritionally adequate and safe foods) and live in "food deserts" , which likely contributes to racial differences in dietary patterns. AAs with hypertension, a leading cause of CKD in the U.S., are less likely to follow a Dietary Approaches to Stop Hypertension (DASH) trial accordant diet than are whites, despite AAs being shown to potentially receive the greatest blood pressure benefit from the DASH diet. Further, AAs are less likely to follow diets rich in fruits and vegetables (base-inducing diets), despite recently emerging evidence that such dietary patterns may lead to favorable kidney outcomes including reductions in markers of kidney damage (i.e. albuminuria).

There is markedly lower availability of components of the DASH diet recommended foods, such as fresh fruits and vegetables, skim milk and whole grain foods, in predominantly AA and lower-income neighborhoods as compared with white and higher-income neighborhoods.  Personally-tailored interventions promoting the DASH diet while addressing barriers to accessing healthful foods could substantially lessen the burden of hypertension and CKD among low SES AAs.

We propose to build upon the encouraging results of our pilot study, "The Five-Plus Nuts and Beans Trial" (*Am J Prev Med*, 2015) which was conducted as a partnership between Johns Hopkins investigators, a community supermarket, the Baltimore City Health Department's "Virtual Supermarket" program, a community-based clinic and a highly engaged Community Advisory Board. This trial tested the effects of a dietary approach to increase consumption of a central feature of the DASH diet--high potassium foods (fruits, vegetables, nuts and beans). A total of 123 AA patients with controlled hypertension recruited from a community-based clinic, were provided personalized dietary advice, assistance with grocery ordering and delivery, and \$30 per week worth of high potassium foods for an 8-week period. With this approach, we demonstrated statistically significant increases in consumption of fruits, vegetables, potassium, magnesium and fiber, and decreases in sodium intake. Also, there was a 14% reduction in urinary albumin excretion overall, and a 30% reduction among patients with significant albuminuria at enrollment. The trial had 100% follow-up on outcomes.

Our current proposal will build on the established partnerships, existing infrastructure and encouraging results of the pilot trial. We propose a longer (1 year) intervention, and the inclusion of AA participants with hypertension (controlled or uncontrolled) plus mild/moderate CKD—a population at very high risk of the adverse effects of diets low in potassium and high in sodium.

Principal Investigator: [name], ScM

Application Number: IRB00122943

2. Objectives (include all primary and secondary objectives)

# **Primary Objective:**

1. To test the hypothesis that delivery of nutritional advice to adopt the DASH diet and \$30 per week worth of potassium-rich foods, tailored to personal choices and availability in neighborhood stores of patients recruited from community-based clinics, will reduce urinary albumin excretion in low SES AAs with hypertension and CKD.

# **Secondary Objectives:**

- 1. To determine if our intervention lowers blood pressure
- 2. To conduct exploratory analyses related to the effects of the intervention on:
  - a) subgroups defined by gender, age, diabetes status, and level of albuminuria
  - b) potential mediating variables (e.g. antihypertensive medication type, weight changes, etc.)
- 3. To pursue mobile platforms for food selections (i.e. smartphone applications)
- 4. To estimate direct costs of broadly implementing the intervention and conduct a cost analysis
- 5. To develop a dissemination plan with community partners to ensure sustainability
- **3. Background** (briefly describe pre-clinical and clinical data, current experience with procedures, drug or device, and any other relevant information to justify the research)

[name] [name] and our study team led the pilot trial, the "Five-Plus Nuts and Beans" Trial which previously tested the impact of a community-based dietary intervention (Am J Prev Med, 2015). In this trial we tested the effectiveness of coach-directed dietary advice and assistance with weekly online ordering and purchasing of high potassium foods (\$30/week) delivered by a community supermarket to a neighborhood library, and tested other outcomes in urban African-American adults with controlled hypertension. We recruited patients from an urban primary care clinic in Baltimore MD and implemented the trial in partnership with a community supermarket and the Baltimore City Health Department. Advised to do so by our CAB/community partners, participants in the control group received a printed DASH diet brochure along with a debit account of equivalent value to that of the intervention (DASH-Plus) group at the same community supermarket. We randomized 123 participants and achieved 100% follow-up. At baseline, mean (SD) age was 58.6 (9.5) years, 71% were female, screening BP was 131.3 (14.7)/77.2 (10.5) mmHg, BMI was 34.5 (8.2) kg/m2, and 28% had diabetes. Self-reported fruit and vegetable intake of 3.5 (1.8) servings/day and estimated potassium intake of 2.7 (0.9) grams/day were well below recommended intakes. Compared to the control group, the DASH-Plus group increased self-reported consumption of fruits and vegetables by a mean (95% CI) of 1.4 (0.7, 2.1) servings/day and an estimated intake of potassium by 0.4 (0.1, 0.7) grams/day. DASH-Plus compared to control resulted in a significant increase in urine potassium excretion of 19% (1, 38)% and lower urine sodium excretion -20% (-38, -3)% (Figure 4). Also, there was a 14% reduction in albuminuria overall, and a 30% reduction among the subset of patients with significant albuminuria at enrollment. While we were underpowered to detect a BP effect at 8 weeks, we concluded that the Five-Plus intervention increased consumption of fruits and vegetables and excretion of urine potassium (an objective marker of potassium intake), and decreased excretion of urine sodium (an objective marker of sodium intake). Recognizing the needs of AAs with or at risk for CKD in Baltimore, and the lack of existing clinical trials of lifestyle modifications for AAs with CKD, we proceeded to develop an approach for AAs with both hypertension and mild/moderate CKD. Here, we describe plans for this intervention.

# 4. Study Procedures

a. Study design, including the sequence and timing of study procedures (distinguish research procedures from those that are part of routine care).

This study will be a single center, randomized controlled trial with 2 parallel arms to test the hypothesis that delivery of nutritional advice to adopt the DASH diet and \$30 per week worth of potassium-rich foods, tailored to personal choices and availability in neighborhood stores of patients recruited from community-based clinics, will reduce urinary albumin excretion in low SES AAs with hypertension and CKD. The primary outcomes are change in ACR as a marker of kidney damage and change in systolic SP. Secondary outcomes are other dimensions of blood pressure (DBP, lipid levels (total cholesterol, LDL-C, HDL-C, and triglycerides); glucose, and Framingham Risk Score.

We anticipate enrolling 150 self-identified African American adults who are above the age of 21 diagnosed with hypertension and mild/moderate CKD based on the presence of albuminuria [urinary albumin-to-creatinine ratio (ACR) >30 mg/g] with or without eGFR 30-59 ml/min/1.73m². Based on the results of the Five-Plus pilot study, the ACT study and the CKD prevalence study by [name] et al , we anticipate ~25-30% of those with hypertension will have albuminuria and would be eligible for participation. All 150 participants will be randomly assigned to one of two groups: 1) Self-Shopping DASH diet advice group (S-DASH) or 2) Coaching DASH diet advice group (C-DASH) with \$30/week allowance for the purchase of high potassium foods from a local grocer.

# 1. Self-Shopping DASH diet advice Group (S-DASH):

#### Phase 1 (Months 0-4)

The S-DASH group will receive printed patient-centered materials on the DASH diet and chronic kidney disease. Participants will also receive \$30/week allowance for the purchase of the foods of their choosing from a local grocer (Klein's ShopRite stores of Maryland).

# Phase 2 (Months 5-12)

S-DASH participants will be asked to continue to follow the dietary advice provided. They will not be provided a food allowance during this phase.

# 2. Coaching DASH diet advice group (C-DASH):

#### Phase 1 (Months 0-4):

The C-DASH intervention will be a patient-tailored program, delivered by a study coach that is trained by a dietitian, which emphasizes key self-management behaviors – diet and self-monitoring. The C-DASH intervention will consist of a 1-hour one-on-one session with the study coach at randomization.

Thereafter, the study coach will meet with the participant at 1 month followed by phone calls only. Fifteen minute calls with participants will be weekly. During these interactions the study coach will build upon the participants' strengths and provide positive reinforcement of the progress being made.

Principal Investigator: [name], ScM

Application Number: IRB00122943

The C-DASH group will purchase \$30 worth of fruits, vegetables, nuts and beans through the study coach to reach a certain goal of potassium intake daily. The target for purchases will be a goal of 17,000 mg/week of potassium in order to increase dietary intake of potassium to 4.7 grams per day (DASH diet target) based on an estimated daily baseline intake of 2.4 g/d in this population. ShopRite will provide free packaging of food orders and foods will be delivered for pick up to Sisters Together And Reaching (S.T.A.R.) community center on [name] or by arrangement.

# **Phase 2 (Months 5-12):**

Participants will be maintained in their assigned group. The C-DASH group will be advised by the study coach on how to maintain the high potassium diet in their home food environment. Between months 5-12, there will be calls as needed, not to exceed six phone calls during Phase Two with the study coach. In addition to assessing diet and providing educational materials, the study coach will assist each participant in setting goals, provide advice and arrange follow-up to monitor progress. Customizable, literacy sensitive modules about nutrition, including the DASH diet, developed by our study dietitian, will be used by the study coach to guide the discussion.

### **Participant Recruitment:**

For this trial, recruitment will be conducted at the Johns Hopkins Community Physicians Sites (e.g. East Baltimore Medical Center or Remington) the Johns Hopkins Outpatient Center (JHOC) and the Johns Hopkins Prohealth Clinical Research Unit. We plan to implement the following recruitment methods in order to meet our recruitment goals:

- 1. We will rely primarily on clinical databases (e.g. EPIC), sorted on age and diagnosis of hypertension; and on African American patients with hypertension who have previously participated in studies that included the investigators (Five Plus Nuts and Beans Trial (NA\_00051935) or Achieving Blood Pressure Control Together (ACT) trial (NA\_00078591), and who indicated willingness to be contacted for future studies. Additionally, patients under the direct care of the PI or co-investigators may be directly referred to the study if they have given their permission to be contacted by the study team.
  - a. For the patients described in #1 above, the study team will mail invitational letters, along with a stamped, self-addressed reply card. The addresses are typically available, either as part of the query of the clinical database or from the chart screening. There will be a checkbox for participants to let us know if they are not interested in participating.
  - 2. We plan to contact participants who do not have a direct clinical relationship with the physicians on the research team by pulling a list of potentially eligible participants from EPIC based on the inclusion criteria. We will then sort the list of eligible participants by provider at East Baltimore Medical Campus (EBMC) and Johns Hopkins Remington. Once the sorted list has been generated, we will ask
  - Johns Hopkins providers to review the lists and indicate if any of their patients on the list should not be contacted for the study (e.g. patient had a recent severe illness). Once the providers have agreed on the list, we will then contact the potentially eligible participants.

Principal Investigator: [name], ScM

Application Number: IRB00122943

3. We plan to contact individuals who respond 'yes' on the reply and those individuals who do not return the reply card. We will contact persons by phone in order to ascertain their level of interest. Our study coordinator, [name], will be the primary contact. For those persons who express interest, we will then schedule the eligibility visit.

4. During the eligibility visit, participants will be approached by a study team member ([name]) in the privacy of an exam room at the patients' clinic, regarding their interest in participation in the study.

**Study Design** (Refer to Table 1 and Table 2 as references):

**Screening Visits:** The study visits will begin with two initial screening visits after recruitment to determine the eligibility and commitment to the research study. During the first two screening visits, the study research team will determine if the interested participant is eligible to participate in the study (see Inclusion/Exclusion criteria). The research team will proceed with discussing the protocol, and obtain consent for access to contact information, blood pressure measurements, medication and medical history review, obtaining weight measurements, review eating habits, collection of spot urine samples, and blood samples.

Once the informed consent has been obtained, the following tests and procedures will be done:

- review the informed consent form
- ask to provide medication and medical history
- dietary assessment (review eating and other habits)
- ask to provide contact information
- ask to provide demographic information
- collect weight measurements
- measure blood pressure
  - collect spot (random) urine samples:
    - the study team will carefully review instructions with the participant
    - measure the albumin, urine potassium, urine sodium and urine creatinine

Randomization Visit: Upon confirmation of eligibility and completion of an up to two month runin and the informed consent process, participants will be randomized in a 1:1 ratio to the self-shopping DASH diet advice group (S-DASH) or the coaching DASH (C-DASH) diet advice group with \$30 per week in high potassium foods from a local grocer. Randomization will be performed using a web-based, password-protected, software set up to ensure authorized access to group assignment, restricted to designated study personnel. The randomization protocol will be in variable blocks (3 and 6) after stratification by gender, using the Moses-Oakford algorithm, adapted for SAS statistical software. The research team will convey randomization assignment to participants. At this study visit, the following will be obtained/performed:

- medication history review
- measure weight measurements
- measure blood pressure

Principal Investigator: [name], ScM

Application Number: IRB00122943

**Follow-up Visit #1 (Month "1"):** The participant will be asked to come to a Johns Hopkins Community Physician Site (e.g. East Baltimore Medical Center) or the Johns Hopkins Outpatient Center for three in-person follow-up visits at 1, 4, and 12 month(s) after the randomization visit. At this study visit, the following will be obtained/performed:

- medication history review
- dietary assessment (review eating and other habits)
- measure blood pressure
- collect spot (random) urine samples:
  - The study team will review instructions with the participant
  - measure the albumin, urine potassium, urine sodium and urine creatinine
- collect blood samples:
  - collect 8.5 cc (less than 2 teaspoons) of blood. The study team will ask the participant not eat or drink anything except water before the blood sample is collected if he/she has not done so during the first screening visit.
  - measure the creatinine, potassium, glucose, and cholesterol.

**Follow-up Visit #2 (Month "4"):** This study visit will be identical to the Month "1" study visit. An additional urine sample will be collected within one month of the follow-up visit.

Follow-up Visit #3 (Month "12"): This study visit will be identical to Month "4" study visit.

**Telephone Calls:** If research participants are randomized to the C-DASH group, telephone calls will be included throughout the intervention of the study. To monitor and improve the study programs, we may record some interviews and may ask experts from the study to listen to some of the counseling sessions. In the first 4 months (Phase 1), the C-DASH group will have fifteen minute telephone calls with a study team member which will occur every week for the first two months, then bi-weekly for two months. In months 5-12 (Phase 2), the calls will occur every other week for the first 2 months, and then on a monthly basis for a total of no more than 6 calls.

Questionnaires: The study team will collect questionnaire data including a demographic/medical history questionnaire that provides a self-report of sociodemographic factors (e.g. age, gender, health insurance status, income, employment, education level, food insecurity), current health status (e.g. post-menopausal status, presence of diabetes, cardiovascular disease), and health habits (e.g. tobacco use). Medication use will be collected at baseline and during follow-up visits. The primary interest are medications used to treat hypertension, diabetes and hypercholesterolemia.

**Dietary Assessment:** Fruit, vegetables, fiber, sodium and potassium intake will be assessed at each visit using the Block Brief screener. The screeners are self-administered, it is used to assess intake over the preceding month, and estimates micronutrient intake including dietary potassium and sodium.

**Fasting glucose, lipids and uric acid**: Fasting blood collections will occur in the morning after a minimum 10 hour fast. Serum will be collected during screening visits, month 4, and month 12. From the fasting blood specimen, estimated GFR, glucose, total cholesterol (TC), HDL cholesterol (HDL), triglycerides, and potassium will be measured. LDL cholesterol (LDL-C) will be estimated by the equation (LDL=TC-HDL-triglyceride/5) 54.

Principal Investigator: [name], ScM

Application Number: IRB00122943

**Urinary sodium and potassium:** From the spot urine collections for urine albumin-to-creatinine samples, urine sodium and potassium excretion will be collected to estimate group compliance with dietary aspects of the intervention.

Table 1:

Questionnaires Table		Phase 1 (0-4)			Phase 2 (5- 12)		
Visit	Pre Screen	SV1	SV2	RV	FV01	FV04	FV12
Months				0	1	4	12
Telephone Prescreening Script	X						
Informed Consent Form		X					
Contact Information	X	X	X	X	X	X	X
Demographic Questionnaire			X				
Medical History		X			X	X	X
Medication Questionnaire		X	X	X	X	X	X
Block Fruit, Veg, Fiber Screener			X			X	X
Block Na Screener			X			X	X
Food Security Questionnaire 			X				X
Short Housing Instability Questionnaire 21,22,23			X				
Eating Habits Questionnaire			X				
Internet Use Survey  /Technology Use Survey 			X				
Depression Patient Health Questionnaire (PHQ-8) 		ТН	X			X	
Generalized Anxiety Disorder Scale (GAD-7) 		ТН	X			X	
Perceived Stress Scale (PSS-10) 		TH	X			X	
Perceived Stress Scale (PSS-10)  Discrimination Scale 		TH	X				
Height Measurement		X					
Weight Measurement		X		X		X	X
Blood Pressure Measurement		X	X	X	X	X	X
Comprehensive Metabolic Panel (fasting)			X		X	X	X
Hemoglobin A1c			X			X	X
Urine (Potassium, Sodium, Creatinine, and Albumin)		X	X		X	X 	X 

Table 1 Legend:

<sup>2 Participants will provide two urine samples at two different point of times

TH: Participants will take home documents to complete

Principal Investigator: [name], ScM

Application Number: IRB00122943

Study duration and number of study visits required of research participants

The study will require 6 in person visits and up to 25 telephone (15 minutes only) calls over the course of 12 months.

b. Blinding, including justification for blinding or not blinding the trial, if applicable.

Participants will know their intervention assignments, as will study staff involved in delivering the interventions. However, study staff involved in follow-up data collection will be kept masked to participants' randomization assignments, and all intervention staff will be kept masked to participants' study measurements.

c. Justification of why participants will not receive routine care or will have current therapy stopped.

Participants will continue with their routine clinical care without interruption.

d. Justification for inclusion of a placebo or non-treatment group.

N/A. Our intervention group will be compared to a usual care group that receives \$30/week food allowance for 4 months.

- e. Definition of treatment failure or participant removal criteria. Participants who develop an exclusion criteria (e.g. stages 4 or 5 of CKD) will be removed from the study prematurely and documented correctly.
- f. Description of what happens to participants receiving therapy when study ends or if a participant's participation in the study ends prematurely.

If a participant chooses to withdraw from the research study, study personnel will inform the participant that compensation from the study will be held, due to prematurely ending participation.

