# 7. Study Statistics

a. Primary outcome variable

**Primary Outcome Variable**: The primary outcome variable for this study is change in albuminuria.

b. Secondary outcome variables.

**Secondary Outcome Variable:** The secondary outcome variable for this study will be change in blood pressure, glucose, and weight.

c. Statistical plan including sample size justification and interim data analysis.

The trial has sufficient resources and adequate power to enroll 150 participants, who will be randomly allocated in equal proportions to the 2 groups: **Group A:** Self-Shopping DASH (S-DASH) diet advice group. **Group B:** Coaching DASH (C-DASH) diet advice group. The primary contrast is the difference in the percent change in (B vs. A) in urine albumin excretion (Urine Albumin to creatinine ratio, mg/g: UAlb/Cr mg/g). We used the standard deviation of the percent difference in the Urine Alb/Cr (post-pre/pre) of 63% and 53% in the intervention arm and the control arm, respectively. These variance estimates are from our pilot study (Five, Plus Nuts and Beans) published in 2016. The pilot trial enrolled African American patients with hypertension (similar to our eligibility criteria). Although albuminuria was not an eligibility criterion, 17 of 123 randomized had albuminuria (UAlb/CR ≥30 mg/g).

Principal Investigator: [name], ScM

Application Number: IRB00122943

Power calculations for our trial are based on a basic model that compares (4 month - baseline) differences among treatment groups (**Table**). The trial has 80% power to detect a treatment effect of 20% difference between arms at  $\alpha = 0.05$  if we enroll 150 participants. For this estimate, we set the correlation between

baseline and follow-up at 80%. This is a conservative estimate as the correlations of the log Alb/Cr between pre and post measurements in the pilot trial was 0.92 and 0.82 in the intervention and the control group, respectively. The weaker correlation in the intervention group would be expected, as variability in response to treatment in this arm would be greater. These treatment effects are achievable. In the pilot trial, the effect size noted was a ~39% difference (N=17) between the 2 arms in the subgroup with UAlb/Cr ≥30 mg/g at baseline. In the ACT Trial (a second trial of blood pressure management strategies in African Americans with uncontrolled

Net treatment	Power for	Sample
effect, % difference	single test	size
in UAlb/Cr	at $\alpha$ =0.05	needed
20%*	0.8	148

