# **Analysis Plan**

This trial is a randomized trial that tests the effects of an innovative intervention against a minimal intervention on a selected set of outcomes. The primary contrast is (A vs. B) in Urine albumin excretion (**Primary Specific Aims**). For secondary analyses, we will test the contrast for reducing blood pressure, glucose, and weight (**Secondary Aim**). The analysis will be conducted under the intent-to-treat principle for both the Primary and the Secondary Aims before any supplemental analyses are conducted.

For the **Primary Aim**, groups will be compared using within-person differences in outcome levels obtained on those diets. Because we anticipate some dropouts (although there were none in the pilot), we will conduct our primary analysis using mixed effects modeling (likelihood) and multiple imputation approach under the missing at random (MAR) assumption. We will adjust for baseline UAlb/Cr which should increase our power and account for any power lost by drop-outs. We will then carefully examine all available data and build sensitivity analyses using clinically sensible missing scenarios to evaluate the potential impact by non-ignorable missing data. A parallel approach will be used for **Secondary Outcomes.** Distribution of data will be checked and transformed where appropriate. Other outcome variables will be analyzed with a similar approach. Adjustments for baseline variables will be made, where appropriate, in multivariable analyses. Ninety-five percent confidence intervals of the estimated mean differences will be constructed for each outcome.

\*\*SD of change of 49% (Sontrop JM et al., 2016

Principal Investigator: [name], ScM

Application Number: IRB00122943

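### Randomisation is stratified by gender, but the primary model does not commit to gender: a small, conservative loss of precision that one sentence would remove

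*Combined protocol and SAP*

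**What the plan says.** Section 4, Randomization Visit, sets the ratio ("participants will be randomized in a 1:1 ratio") and the method ("The randomization protocol will be in variable blocks (3 and 6) after stratification by gender"). Gender is the only stratification factor. Nothing in the documents says how many of each arm a block of 3 contains.

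The Analysis Plan in Section 7 describes the primary analysis as "mixed effects modeling (likelihood) and multiple imputation approach under the missing at random (MAR) assumption". It names one covariate: "We will adjust for baseline UAlb/Cr which should increase our power and account for any power lost by drop-outs". A general clause follows: "Adjustments for baseline variables will be made, where appropriate, in multivariable analyses". For the remaining outcomes it adds: "Other outcome variables will be analyzed with a similar approach". Gender is named neither as a model term nor as an imputation variable. It appears elsewhere as an exploratory subgroup (Section 2, Secondary Objectives) and as a questionnaire item (Section 4, Questionnaires).

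**The concern.** Stratifying by gender keeps the share of women nearly equal in the two arms, so the estimated difference varies less from trial to trial. That gain shows in the reported standard error only if the model contains gender. Without it, variation due to gender stays in the residual, the standard error describes a less balanced design than the one used, and the test rejects slightly too seldom.

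What is at stake is a little precision, and a covariate choice left open until the data are in hand. The plan itself counts on baseline adjustment to offset power lost to dropouts, so it is odd not to name the one factor already balanced by design. The same gap carries over to blood pressure, glucose and weight, because those models follow the primary one.

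**Working it through.** **Inputs.** From the plan: 150 participants, 1:1, α = 0.05 (taken as two-sided; the plan does not say), and Section 7c's claim, "The trial has 80% power to detect a treatment effect of 20% difference between arms". From Section 3 (pilot): "71% were female", used as an assumed share of women. Assumed, because the documents give nothing: R², the share of the variance in albuminuria change, after baseline adjustment, that gender explains.

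**The plan's own figure.** Section 7c gives N = 148 for a 20% difference. The listed SDs of 63% and 53% pool to √[(0.63² + 0.53²)/2] = 0.582. At two-sided 0.05 and 80% power that gives N = 266 with no correlation factor. With correlation r = 0.8 it gives 108 using the factor 2(1−r) and 96 using 1−r². On the log(0.8) scale it gives 214. I could not reproduce 148. This point does not depend on it: I start from the stated 80% power. I use 148 only to back out an implied SD: √[74 × 0.20² / (2 × 2.802²)] = 0.434.

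**Formulas.** Let c = √(1 − R²). The planned 80% power means effect/SE = 1.960 + 0.842 = 2.802.
- Reported SE without gender, relative to the correct one: 1/c
- Actual type I error without gender: 2[1 − Φ(1.960/c)]
- Power without gender: Φ(0.842/c)
- Power with gender: Φ(2.802/c − 1.960)
- Gender gap implied by R²: 0.434 × √R² / √(0.71 × 0.29)

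| R² | SE too wide by | Type I error without gender | Power without gender | Power with gender | Points forgone | Gender gap needed |
|---|---|---|---|---|---|---|
| 0% | 0% | 0.050 | 80.0% | 80.0% | 0 | 0 |
| 1% | 0.5% | 0.049 | 80.1% | 80.4% | 0.3 | 9.6 points |
| 2% | 1.0% | 0.048 | 80.2% | 80.8% | 0.5 | 13.5 points |
| 5% | 2.6% | 0.044 | 80.6% | 82.0% | 1.4 | 21.4 points |

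In reverse, a 10-point gender gap gives R² = 0.10² × 0.71 × 0.29 / 0.434² ≈ 1.1%. The SE is then about 0.55% too wide and about 0.3 power point is forgone.

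**Check by simulation.** These runs used 150 participants, 71% women, and stratified blocks of 3 and 6 with a random majority arm in each 3-block. At a deliberately large R² of 10%, the model without gender reported a mean SE of 0.0710 against a true spread of 0.0682 (type I error 0.040). With gender the figures were 0.0674 and 0.0678 (0.051). The direction is confirmed. A separate set of runs gave power without/with gender of 79.5/80.0% at R² = 2% and 79.2/81.0% at 5% (Monte Carlo error about 0.45 point). Those levels lie about 0.7 to 1.4 points below the formula. The normal approximation explains part of this: the t-based figure for the 80% starting point is 79.48%. I therefore rely on the differences, not the levels.

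**Cost of adding gender if it explains nothing.** The critical t moves from 1.9762 (147 df) to 1.9763 (146 df), and t-based power from 79.482% to 79.479%.

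**Blocks of 3.** Three cannot be split equally between two arms. If the majority arm is random in each 3-block, the split averages 75:75, with 71 to 79 in one arm (95% range). If the majority arm alternates, the range is 73 to 77. With SE² proportional to 0.63²/n(C-DASH) + 0.53²/n(S-DASH), 75/75 gives 0.009037 and 71/79 gives 0.009146. Power moves from 80.0% to 79.5% at worst. If every 3-block favoured the same arm, the split would be about 83:67. With a common SD of 0.434, power would then be 80.1% against 80.6% at 75:75.

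**The case against.** The strongest reply is that the plan already allows gender under its clause on baseline variables, and that leaving it out errs on the safe side. Both parts stand. The clause does permit gender, so this is a missing commitment and not a contradiction. With complete follow-up the estimate is unbiased and type I error is at or below 0.05. If gender explains nothing, nothing is lost. What the reply does not meet is that permission is not pre-specification, and that committing costs essentially nothing.

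A second reply is that large losses need implausible inputs. That stands too. An R² of 10% would be worth 150 × 0.10 = 15 participants, but it needs a gender gap of about 30 points, well above the 20% effect the trial is built to detect. Nothing in the documents supports a gap of that size.

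A reader might go further and infer that omitting gender biases the result, since the Analysis Plan expects dropouts and assumes missing at random. That would need dropout by gender to differ between arms and gender to predict change. The documents give no dropout rate by arm or gender, the pilot had complete follow-up, and the plan promises sensitivity analyses for non-ignorable missingness. The imputation variables are not listed, so gender's absence from them is not established either. The possibility is a reason to name gender in the imputation model, not evidence of bias.

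**Conclusion.** The point holds as a minor, free improvement. Gender is the sole stratification factor, and the primary model does not commit to it. For an assumed R² of 0 to 5%, the standard error is 0 to 2.6% too wide and 0 to about 1.4 power points go unused. A 10-point gender gap, at about 0.3 power point, is a more plausible case than the top of that range. These sizes rest on assumed values of R², on the plan's stated 80% power taken as given and, for the gaps, on 71% women and an SD of 0.434.

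The block-of-3 point is mainly a reporting gap. A reader might infer that blocks of 3 defeat the 1:1 allocation. The documents do not support that: Sections 4 and 7c both state equal allocation, and a random or alternating majority arm delivers it on average. What is missing is the rule for filling those blocks.

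**What to change.** In the Analysis Plan, before any comparison by arm is seen, state that the primary model includes arm, baseline UAlb/Cr and gender (the stratification factor) as fixed effects, that gender is also in the imputation model, and that the secondary-outcome models do the same. This takes one sentence and one degree of freedom. It needs no new data, because gender is already recorded and used to randomise, and it can be done at any stage of enrolment.

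Separately, check the randomisation list actually used, state how its blocks of 3 are filled, and report the achieved allocation overall and by gender. If the majority arm was random or alternating, documenting that is enough. The block sizes need not change for validity.
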